8.1.1 Child-level

The primary (i.e. dental attendance) and secondary outcomes (i.e. new decay, oral hygiene, frequency of sweet food and drinks, oral health-related quality of life, and dental-related costs) are also implementation measures of effectiveness. Child medical illness is a confounder.

Child dental attendance (i.e. receipt of dental care) will be assessed through:

- Clinical dental screenings will be performed at all 3 WCVs (T_0 , T_3 , and T_6) by a trained and calibrated dental hygienist according to the International Caries Detection and Assessment System (ICDAS). The screenings will be used to identify a change in oral health status between WCVs #1 and #2 (T_0 and T_3) and WCVs #2 and #3 (T_3 and T_6) which is defined as a restoration (ICDAS ≥ 3) or extraction of ≥ 1 tooth previously identified with an active ICDAS lesion code ≥ 3 at T_0 or T_3 that would not be exfoliated naturally based on child's age. See ICDAS Assessment form (Appendix E). More details on the screening and decision algorithm will be outlined in the MOP Section 5.
- B2: Dental Attendance & Cost Questionnaire: Study staff will contact caregivers 6 months after WCVs #1 and #2 (T_1 and T_4) to ask whether their child had a dental visit or if they made a dental appointment for their child since the previous WCV (Appendix E).
- Medicaid claims files: Data will be abstracted by study staff to verify child's receipt of dental care after each WCV (T_1 , T_4 , and T_7) and entered on the Medicaid Claims Abstraction form. Current Dental Terminology (CDT) codes used for billing will be used to determine if the child received preventive or restorative procedures in the past 12 months. Dental emergency department (ED) visits will be identified by linking diagnosis codes (Appendix E) to ED claims using the International Classification of Diseases, Tenth Revision, Clinical Modification (ICD-10-CM). See Medicaid Claims Abstraction form (Appendix E) for preventive and restorative CDT codes and ICD-10-CM codes.
- COVID-19 Questionnaire: At WCV3, actively enrolled parent/caregivers will complete a short (7 item) COVID-19 Questionnaire which asks if they have altered their behavior related to taking their child to the dentist due to the COVID-19 pandemic.

Secondary outcomes and child medical illness (i.e. confounder) will be assessed as follows:

- A newly carious tooth is defined as any tooth receiving an ICDAS lesion code ≥ 3 that received a sound code on the previous dental screening or any tooth surface with an ICDAS filling code ≥ 3 that previously did not have one. Number of teeth with new decay or filling will be assessed through the clinical dental screenings (T_0 , T_3 , and T_6) and recorded on the ICDAS Assessment form (Appendix E).
- Questions on frequency of tooth brushing (NHANES III)(CDC), frequency of consumption of sweet food and drinks (NHANES 2009-2010; Youth Risk Behavior Survey 2017)(CDC, 2017; CDC, 2014), and the 13-item Early Childhood Oral Health Impact Scale (ECOHIS)(Pahel et al., 2007) will be used to measure oral hygiene, frequency of sweet food and drinks, and oral health-related quality of life (OHRQoL), respectively. Higher scores on

the ECOHIS indicate poorer OHRQoL. These questions are included on the A2: Parent Questionnaire (Appendix E) which will be completed at all 3 WCVs (T_0 , T_3 , and T_6).

- Direct dental costs include costs of preventive and restorative procedures, and dentalrelated ED visits. These costs will be abstracted from Medicaid claims files as part of the verification of child's dental care receipt (described above) and recorded on the Medicaid Claims Abstraction form. Non-dental direct costs (transportation) and dental indirect costs (time away from work, household, or leisure activities) are measured using questions adapted from the Annotated Cost Questionnaire (Thompson & Wordsworth, 2001) which are incorporated into the B2 Follow-up Questionnaire. The B2 Questionnaire will be administered after WCVs #1 and #2 (T_1 and T_4). Study staff will administer the cost questionnaire at WCV #3 (T_6) to identify any lags in receipt of dental care. Cost data from Medicaid claims files will be abstracted at 3 time points (T_1 , T_4 , and T_7). See the Annotated Cost Questionnaire and Medicaid Claims Abstraction form (Appendix E) for more details.

Table 8.1.2 Cost elements and sources

Cost Category	Cost Element	Source
Implementation/ training costs	Training providers in communicating oral health facts	Study training records/logs
	IT system modifications	Vendor invoices, clinic personnel time logs
	Staff training	Study staff time/training logs
Intervention costs	Time required to provide education and give prescription	Review of audiotaped encounters
	Cost of dental prescription pads, flip charts, pocket cards	Study/practice expense records
Dental costs	Direct dental costs - Dental utilization costs (including emergency)	Medicaid claims data for participants
	Non-dental direct costs (e.g. transportation to dental visits)	Annotated Cost Questionnaire
	Dental Indirect costs (e.g. time away from work, household, or leisure activities)	Annotated Cost Questionnaire

Note: If training/study staff time logs conflict for a given activity, the arithmetic mean of the two figures will be used in analysis.

- Medical illness data will be abstracted from the child's medical charts (i.e. EMR) and classified into a 10 clinical risk grouping system (Chi & Rakljos, 2012). EMR abstraction will be performed by study staff after each WCV (T_0 , T_3 , and T_6). See EMR Abstraction form (Appendix E).

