2.2 Rationale

Ten million U.S. preschool and school-age children have untreated caries and profound disparities exist by race, socioeconomic status, and geographic region. Our studies in Cleveland have found that school dental screenings have not been effective in stimulating dental attendance ([name] et al., 2012) despite eligibility under the Affordable Care Act and coverage through Medicaid. Our pilot study results among 86 three to six year old Medicaid-enrolled children indicate that 36% (31 out of 86) had untreated dental caries (cavitation), much higher than the national average of 18% (Dye et al. 2017).

There are three core parent (or caregiver) issues: (1) awareness of importance of caries-free primary teeth; (2) understanding dental caries as a chronic disease that can be present even without symptomatic tooth pain; (3) navigating resources for dental care access. Thus, an accurate perception of dental caries is required for parental self-management strategies to take

care of their child's oral health needs. Also important is that parent/caregivers receive consistent OH facts from primary care settings, where young children are most often seen. In one study, two to five year old children were 3 times more likely to visit a dentist when advised by a primary health care provider, but this study also reported that low-income families were less likely to be advised (Beil & Rozier, 2010).

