3.2.1 Primary Outcome Measures

The primary outcome will be dental attendance (receipt of dental care as yes/no, and number of visits). The primary outcome will be determined through a hierarchical process where Medicaid dental claims data (Current Dental Terminology (CDT) codes for preventive or restorative procedures in the past 12 months) would be the primary measure, followed by assessments through clinical dental screenings (restoration or extraction between WCVs #1 and #2, and between WCVs #2 and #3), conducted by calibrated examiners (See Section 14.2).

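### Where the screening tier decides a child-year, section 8.1.1 appears to count a filling as attendance only on a tooth already coded as a lesion ≥3, while section 3.2.1 counts any restoration

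*Combined protocol and SAP*

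**What the plan says.** Section 3.2.1 sets the structure: "The primary outcome will be determined through a hierarchical process". The first tier is claims: "Medicaid dental claims data (Current Dental Terminology (CDT) codes for preventive or restorative procedures in the past 12 months) would be the primary measure". The second tier is the calibrated clinical screening, described there as "restoration or extraction between WCVs #1 and #2, and between WCVs #2 and #3". Nothing in 3.2.1 refers to the earlier state of the tooth.

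Section 8.1.1 gives the working definition of the screening tier. The screenings look for a change in oral health status between consecutive well-child visits, "defined as a restoration (ICDAS ≥ 3) or extraction of ≥ 1 tooth previously identified with an active ICDAS lesion code ≥ 3". The lesion may have been coded at either of the first two screenings, and a further clause excludes teeth that would be lost naturally at the child's age. Details of the decision algorithm are left to MOP Section 5, which is not in the documents.

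The same section defines new caries from the same screenings and counts "any tooth surface with an ICDAS filling code ≥ 3 that previously did not have one". Section 3.2.2 likewise lists restorations on previously sound teeth among the findings that make up the caries outcome.

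**The concern.** The two descriptions of the screening tier differ for one finding that a screening can see: a filling on a tooth that was coded sound, or below 3, at the previous screening. Under 3.2.1 it is attendance. Under the natural reading of 8.1.1 it is not. A filling cannot be placed without a dental visit, so a rule that ignores it turns a known attender into a non-attender whenever screening is what decides the year.

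The screening tier can matter for several reasons:

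- Section 3.2.1 names it as the second measure but does not say what triggers it: claims unavailable, or claims available but negative.
- Medicaid enrolment is an entry criterion in section 5.1, and no section requires it to continue.
- The claims look-back is 12 months, while the visit windows in sections 7.2.2 and 7.2.3 (Day 365 ± 90 and Day 730 ± 90) allow up to 820 − 275 = 545 days between WCV #2 and WCV #3. Read literally, and depending on when claims are abstracted, a filling early in a long interval could fall outside the look-back.

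At stake is misclassification in the 0/1/2 attendance score. If attenders are missed at the same rate in both arms, the difference between arms shrinks.

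**Working it through.** **1. The rules applied to tooth histories.** This is screening only, with no qualifying claim and no other qualifying tooth. Scores are given as interval 1 / interval 2.

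| Tooth history | Visit took place | 3.2.1 | 8.1.1, natural reading | Caries rule in 8.1.1 |
|---|---|---|---|---|
| Sound at T0, filled at T3, unchanged at T6 | 1/0 | 1/0 | 0/0 | New filling, interval 1 |
| Lesion ≥3 at T0, filled at T3, unchanged at T6 | 1/0 | 1/0 | 1/0 | New filling, interval 1 |
| Lesion ≥3 at T0 and T3, filled at T6 | 0/1 | 0/1 | 0/1 | New filling, interval 2 |

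Only the first row goes wrong. In the second row the filling is present at both T3 and T6. It is therefore not a change between those visits and scores nothing in interval 2.

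**2. When the first row reaches the primary outcome.** All of these must hold:

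- no qualifying claim for that child-year;
- the screening tier is then used;
- a new filling is present on a tooth not previously coded as an active lesion ≥3;
- no other tooth qualifies.

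The documents give no figure for this joint event.

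**3. What the pilot figure does and does not show.** Section 2.2 reports untreated cavitation in 31 of 86 pilot children. 1 − 31/86 = 0.64. If cavitation is taken to mean code ≥3, about 64% of children would have no qualifying tooth at T0, so no year-1 filling of theirs could register on screening under the natural reading. That is the share for whom the rule cannot work in year 1. It is not the share misclassified, which also needs a filling and a missing claim.

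**4. The plan's power, and its sensitivity to missed attenders.** Inputs from section 12.2: 0.46 versus 0.30, two-sided alpha 0.05, pooled z test, 512 per arm, 25% dropout, ICC 0.04, 9 practices per arm.

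- Completers per arm: 512 × 0.75 = 384. Per practice: 384 / 9 = 42.67.
- Design effect: 1 + (42.67 − 1) × 0.04 = 2.667.
- Effective n per arm: 384 / 2.667 = 144.0.
- Power: 0.802, against the stated 80%. The plan's figure reproduces.

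Now suppose a share f of true attenders is missed equally in both arms. The rates become 0.46(1 − f) and 0.30(1 − f), and the difference becomes 0.16(1 − f). Effective n is held at 144.0.

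| f (assumed) | Rates | Power |
|---|---|---|
| 0 | 0.460 vs 0.300 | 0.802 |
| 1% | 0.455 vs 0.297 | 0.796 |
| 2% | 0.451 vs 0.294 | 0.789 |
| 5% | 0.437 vs 0.285 | 0.769 |
| 10% | 0.414 vs 0.270 | 0.733 |

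These values of f are illustrations, because the documents do not give f. The table uses the binary outcome of the power calculation, not the ordinal score of the final analysis.

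**The case against.** **Claims come first.** A billed filling scores as attendance whatever the tooth's earlier code. Section 8.1.1 repeats that CDT codes "will be used to determine if the child received preventive or restorative procedures in the past 12 months", and all children are Medicaid-enrolled at entry. This stands, and it confines the problem to child-years decided by screening. A reader might infer that any child whose sound tooth is filled is scored as not having seen a dentist. The documents do not support that.

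**The sentence is ambiguous.** The clause on natural exfoliation fits extraction only, which suggests that the whole trailing condition, including the prior lesion, may attach to extraction alone. On that reading 8.1.1 counts any new restoration and agrees with 3.2.1. This is a fair reading, though the condition more naturally covers both nouns. Two programmers could code the primary outcome differently, which is itself a reason to settle the wording.

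**The algorithm is in the MOP.** It may already handle this correctly. That cannot be checked here, and the two protocol sections would still need to agree.

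**The caries outcome is a different construct.** It need not use the attendance rule, so the difference between the two is not a contradiction. It does show that the trial expects fillings on previously sound teeth and records them.

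**Double counting.** A reader might also infer that a lesion at T0, filled by T3 and still filled at T6, scores in both intervals, because 8.1.1 refers to a lesion at T0 or T3. It does not: the same sentence requires a change between consecutive visits, and an unchanged filling is not one.

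**Sensitivity against specificity.** Hygienists do not see the baseline results and use no radiographs (section 14.2.1), so a filling overlooked once could later appear new. This is a real but small cost of the wider rule. For extractions, the prior-lesion condition helps separate treatment from other tooth loss, and there is no case here for removing it.

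**Conclusion.** The point holds for the screening tier only. On its natural reading, 8.1.1 is narrower than 3.2.1 for restorations. A claims-negative child with a new filling on a tooth previously coded sound or below 3, and no other qualifying tooth, would be scored as a non-attender for that interval.

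This rests on three assumptions: that the prior-lesion condition covers restorations as well as extractions, that screening decides the year when claims show no visit, and that the MOP does not already say otherwise.

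The size is unknown and may be small. The 64% without cavitation in the pilot should not be read as its magnitude. The stated power of 80% reproduces and no sample size figure changes. The plan has little power above 80% to absorb missed attenders, which is a modest reason to remove an avoidable source of them. The point deserves correction because it sits in the definition of the primary outcome and costs little to put right.

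**What to change.** In section 8.1.1, define screening-based attendance for an interval as follows:

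- **Restorations:** any tooth with a filling code ≥3 at the current screening that had none at the immediately preceding screening, whatever its earlier lesion code.
- **Extractions:** keep the existing prior-lesion and natural-exfoliation conditions.
- **Reference point:** for clarity, replace the reference to T0 or T3 with the immediately preceding screening.

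Align section 3.2.1 and the decision algorithm in MOP Section 5 with this text.

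The cost is a wording change and a change to the derivation. The ICDAS codes are already collected at all three visits, so no new data are needed. The downside is that an old filling missed at one screening and seen at the next would count as a visit.

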8.1.2 Parent/caregiver

Measures at the parent/caregiver-level are mediators (IPQ-RD and self-efficacy) and moderators (socio-demographic characteristics, health literacy, and social support).

- The Illness Perception Questionnaire-Revised for Dental (IPQ-RD) ([name] et al., 2016) is comprised of 5 main cognitive constructs (i.e. identity, cause, timeline, consequences, and cure/controllability) and will be used to assess the impact of the provider-level intervention on caregivers' perception of their child's dental caries. Overall and construct-specific scores will be calculated with higher scores indicating caregivers' less accurate/inaccurate perception of the caries disease process and its chronicity. Caregivers will complete the A1: IPQ-RD before the OH encounter with their provider at WCVs #1 - #3 (T_0 , T_3 , and T_6). The B1: Follow-up IPQ-RD will be completed after WCVs #1 and #2 (T_1 and T_4). See A1: IPQ-RD and B1: Follow-up IPQ-RD in Appendix E.
- Self-efficacy (Detroit Dental Health Project, 2004) will include 9 items in which parents assess their confidence in their ability to take the child to the dentist despite personal barriers. Questions on self-efficacy are included in the A2: Parent Questionnaire (Appendix E) completed at all 3 WCVs (T_0 , T_3 , and T_6).
- Moderators include: caregiver health literacy (Morris et al., 2006), social support (Zimet et al., 1988), and socio-demographics (CDC), i.e. sex, age, race, education, occupation, and marital status. The A2: Parent Questionnaire (Appendix E) includes questions to collect data on all 3 moderators at all 3 WCVs (T_0 , T_3 , and T_6).

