7.2 Parent/Caregiver and Child

7.2.1 Baseline Visit: WCV #1

At WCV #1 (T₀: Day 0)

Before Provider Encounter

- Study Staff will recruit 1024 parent/caregivers and their children from the 18 practices (approximately 56-57 participants/practice) using an in-person approach. Parents/caregivers attending well-child visits with 3-6 year old children will be approached for participation.

- In the waiting area/exam room of the pediatric practice, study staff will review inclusion/exclusion criteria as outlined on the screening survey to determine parent/caregiver and child eligibility (Refer to Sections 5.1, 5.2).
- Review the written consent form with the potential participant; study staff signs the consent form acknowledging that informed consent was reviewed and caregiver signs acknowledging consent was obtained (Appendix C: Consent forms).
- In the waiting area/exam room of the pediatric practice, study staff will obtain contact information.
- In the exam room, caregivers will complete the following self-administered Baseline questionnaires: A1: Illness Perception Questionnaire-Revised for Dental (IPQ-RD) and A2: Parent Questionnaire (Appendix E: Questionnaires & forms).
- In the exam room, dental hygienist will perform child dental screening examination and study staff will record results of the dental screening examination. Results will not be available to the provider, unless the hygienist finds that the child has urgent needs that require immediate attention. (Appendix E: Questionnaires & forms).

During Provider Encounter in the Exam Room

- Caregivers attending WCV's will receive OH information, prescription to take the child to the dentist + list of local Medicaid-accepting dentists from provider, based on study arm.
- Caregivers attending WCV's may have study staff audiotape or directly observe the provider encounter to evaluate provider's delivery of OH communication (for a sample of visits).

After Provider Encounter in the Exam Room/Waiting Area

- Caregivers will provide feedback about the OH information given to them during the medical visit with a short self-administered exit questionnaire (A3: [Appendix E: Questionnaires & forms]).
- Caregivers will be given the B1: Follow-up IPQ-RD (Appendix E: Questionnaires & forms) to be completed and returned (in postage paid envelope or in person, based on participant preference).

After WCV #1 (T₁)

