7.2.2 Follow-up Visit: WCV #2

At WCV #2 (T₃: Day 365 ± 90)

Before Provider Encounter in the Exam Room

- If a different parent/caregiver brings the child to the well child visit and they are the child's legal guardian, consent will be obtained from that parent/caregiver and they will complete all components of the visit.
- Parent/caregivers will complete the following self-administered questionnaires: A1: Illness Perception Questionnaire-Revised for Dental (IPQ-RD) and A2: Parent Questionnaire.
- Dental hygienist will perform child dental screening examination and study staff will record results of the dental screening examination. Results will not be available to the provider unless the hygienist finds that the child has urgent needs that require immediate attention.

During Provider Encounter in the Exam Room

- Caregivers attending WCV's will receive OH information, prescription to take the child to the dentist + list of local Medicaid-accepting dentists from provider, based on study arm.
- Caregivers attending WCV's may have study staff audiotape or directly observe the provider encounter to evaluate the provider's delivery of OH communication (for a sample of visits).

After Provider Encounter in the Exam Room/Waiting Area

- Caregivers will provide feedback about the OH information given to them during the medical visit using a short self-administered exit questionnaire (A3).
- Parents will be given the B1: Follow-up IPQ-RD to be completed and returned within 2 weeks (in postage paid envelope or in person, based on participant preference).

After WCV #2 (T₄):

- **B1 (Day 365 ± 120):** Caregivers will receive telephone calls and text messages from study staff to remind them to complete and return the B1: Follow-up IPQ-RD if it has not already been returned.
- **B2 (Day 545 ± 90):** Caregivers will receive telephone calls and text messages from study staff 6 months after the WCV to complete the B2: Dental Attendance & Cost Questionnaire (Appendix E: Questionnaires & forms).

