8.1.3 Provider

Provider-level measures include mediators (OH knowledge and self-efficacy), a confounder (socio-demographic characteristics), and evaluation of implementation/fidelity (observation and audiotape of OH encounters) and adoption & maintenance (i.e. percentage of enrolled patients given a prescription and list of dentists).

- Providers' OH knowledge and self-efficacy to perform OH activities will be assessed through pre- and post-tests (Appendix E) administered before and after the didactic education session prior to WCV #1 (T_{-1}) and booster sessions before WCV #2 (T_2).
- Providers' socio-demographic characteristics (Appendix E) will be collected at the didactic training sessions prior to WCV#1 (T_{-1}).
- As an evaluation of the implementation/fidelity of the intervention, providers' oral health encounters will be observed or audiotaped by study staff and evaluated using the ParentProvider Communication Checklist (Appendix E), the same standardized skills checklist used during the skills training session (T_0 , T_3 , and T_6).
- Parent/caregivers will evaluate their provider's oral health communication and delivery of prescription and list of dentists on the A3: Parent exit questionnaire (Appendix E) completed at WCVs #1 - #3 (T_0 , T_3 , and T_6). This is also an evaluation of implementation/fidelity.
- Providers' EMR documentation of prescriptions and lists of dentists given will be audited throughout the main trial (T_0 , T_3 , and T_6), based on study arm. The percentage of enrolled caregivers who received the prescription and list of dentists will be calculated as an

evaluation of providers' adoption and maintenance of the provider-level intervention and recorded on the EMR Audit of Practice form (Appendix E).

- Providers will complete structured interviews with a trained moderator on implementation barriers/enablers to evaluate best strategies for dissemination of the oral health intervention. The interviews will be conducted at the pediatric practices at a time convenient for the provider and will contain interview questions to assess relative advantage of the OH intervention, compatibility of the OH intervention with the needs of the adopters, complexity of the OH intervention, trialability, and observability. Interviews will be conducted using zoom if in-person interviews are not possible due to the current COVID-19 outbreak.

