8.1.4 Practice

Practice-level measures include mediators (organization readiness, organizational climate, and practice attitude) and evaluation of adoption and maintenance (percentage of enrolled patients with complete oral health documentation in EMR).

- Mediators of organization readiness and organization climate (Stamatakis et al., 2012) and practice attitudes toward adopting evidence-based interventions (EBI)(Aarons, 2004) will be assessed on the Practice Questionnaire (Appendix E) among leaders and providers from all 18 practices prior to enrollment of caregiver participants (T₋₁).
- Audits of providers' documentation of all 4 questions in EMR will be performed throughout the main trial (T₀, T₃, and T₆), based on study arm. The percentage of enrolled patients with complete documentation (i.e. all 4 questions) will be recorded on the EMR Audit of Practice form (Appendix E) and serve as an evaluation of the practice's adoption and maintenance of systematic documentation of OH in EMR for Arm A.

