help reveal the importance of each of the multiple components of the bundled intervention. For example, we can estimate the proportion of intervention effect mediated by 'compliance' with regard to EMR documentation. A relatively high mediation proportion will suggest efficacy of the corresponding component.

We have previously developed a generalized causal mediation (GCM) analysis methodology and an accompanying R package (Albert & [name], 2011; Albert, Unpublished; Cho & Albert, Unpublished) which we will use to estimate and test each path effect and its proportion of the total intervention effect. The GCM method allows mediators and final outcomes of different types, including continuous, binary, and count (assumed to have normal, Bernoulli, and Poisson or negative binomial distributions, respectively). These options will accommodate the mediators and final outcome (dental attendance, summarized as a binary response) in our model. Each outcome (including mediators) is modeled using a generalized linear model that includes as covariates possible baseline confounders as well as causally preceding variables according to the causal model (as in Figure 4.2.1). The method uses an extended version of the mediation formula and assumes an extended version of the sequential ignorability assumption. (Albert et al., Unpublished) Bootstrap resampling is used to compute confidence intervals and a cluster bootstrap option is available to account for unexplained between-cluster (e.g. provider) variability.

Adjustment for Baseline Characteristics: Estimated intervention effects will be adjusted for the following baseline socio-demographic variables: child's age, race, and caregiver SES, education, and marital status.

Model Assumptions: We will assume that the probabilities of dental care receipt follow a logistic regression model with the included covariates and random effects. Per the standard approach, random effects will be assumed to be independent, normally distributed, and outcomes assumed conditionally independent given the random effects. If multiple random effects (e.g., for different cluster levels) are used, they will be assumed to be independent. For secondary outcomes, analogous assumptions, including the assumption of the correct link function, will be made.

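### Parent self-efficacy has no value between first exposure and year-1 attendance, yet section 12.4 would relate it as a mediator to one undivided binary attendance summary

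*Combined protocol and SAP*

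**What the plan says.** Sections 3.2.3, 4.2 and 8.1.2 name two parent-level mediators: illness perception (IPQ-RD) and self-efficacy to take the child to the dentist.

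- **Self-efficacy.** Section 8.1.2: "Questions on self-efficacy are included in the A2: Parent Questionnaire", at T0, T3 and T6. At WCV #1, before the provider encounter, "caregivers will complete the following self-administered Baseline questionnaires: A1" and A2 (section 7.2.1). At WCV #2, again before the encounter, "Parent/caregivers will complete the following self-administered questionnaires: A1: Illness Perception Questionnaire-Revised for Dental (IPQ-RD) and A2: Parent Questionnaire" (section 7.2.2). Section 7.2.3 repeats this order at WCV #3.
- **Illness perception.** Besides A1 at the three visits, "The B1: Follow-up IPQ-RD will be completed after WCVs #1 and #2" (section 8.1.2).
- **Provider knowledge and self-efficacy.** Tests are "administered before and after the didactic education session prior to WCV #1", and again around the booster at T2 (section 8.1.3).
- **Practice readiness, climate and attitude.** Assessed among leaders and providers "from all 18 practices prior to enrollment of caregiver participants", that is at T-1 (section 8.1.4). The practice row of Table 8.1.1 appears to give T-1 and T2 for these, and T4 and T6 for EMR documentation, which sections 8.1.3 and 8.1.4 audit at T0, T3 and T6. That row is broken in the text available, so its assignments are uncertain.
- **Mediation outcome.** Section 12.4 refers to the "final outcome (dental attendance, summarized as a binary response". It orders variables by the conceptual figure and assumes an extended form of sequential ignorability. It names no time point for any mediator and no attendance interval for any path.

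**The concern.** A mediator has to be measured after the exposure and before the outcome it is meant to explain. For parent self-efficacy, T0 is before exposure, T3 is after all attendance between WCV #1 and WCV #2, and T6 is at the end of follow-up. None of these lies between the first encounter and a two-year attendance outcome.

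A dental visit may itself raise a parent's confidence in arranging one. If the intervention raises attendance by any route, it then raises later self-efficacy as a consequence. A model of two-year attendance on that later value would report part of the effect as mediated even if self-efficacy did nothing.

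Mediation is secondary objective 2, and section 12.4 intends to read a high mediated proportion as a sign that the corresponding component works. A false proportion could therefore influence what is said about how the bundle acts.

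**Working it through.** **Plan's own figure.** Section 12.2 uses 0.46 vs 0.30, two-sided 0.05, pooled z, 80% power, 9 practices per arm, ICC 0.04 and 25% dropout. The unclustered size is [1.96·√(2·0.38·0.62) + 0.842·√(0.46·0.54 + 0.30·0.70)]² / 0.16², which rounds up to 144 per arm. Practice size is m = 144·0.96 / (9 − 144·0.04) = 42.67. Then 9·42.67 = 384 evaluable, and 384/0.75 = 512, as stated. The calculation applies 0.46 and 0.30 to any attendance over two years.

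**Share of a nominal 730-day window gone at each measurement**
- B1 illness perception: at most 120/730 = 16%.
- T3 self-efficacy: 365/730 = 50% (275/730 = 38% to 455/730 = 62% over the visit window).
- T6 self-efficacy: 100% at nominal day 730.

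**Share of eventual attenders who have attended by T3.** Let P be two-year attendance, with independent years of equal risk (assumed). Annual risk is p = 1 − √(1 − P), and the share is p/P.
- Arm A: p = 1 − √0.54 = 0.265; 0.265/0.46 = 58%.
- Arm B: p = 1 − √0.70 = 0.163; 0.163/0.30 = 54%.
- Over the T3 window, with constant hazard, [1 − (1 − P)^(t/730)]/P runs from 42% (Arm B, day 275) to 69% (Arm A, day 455).
- With an assumed between-year correlation of 0.3 to 0.6, the nominal-day share is 64% to 80%.

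**Size of the bias.** These shares are not the bias, so it was simulated. Two-year attendance was 0.30 and 0.46 with independent years. Self-efficacy had no effect on attendance, but year-1 attendance raised T3 self-efficacy by d SD (assumed). Attendance was regressed on arm and self-efficacy by logistic regression, self-efficacy on arm by linear regression, and the indirect effect came from the mediation formula. Clustering was ignored.

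| d | False share, two-year outcome | Year-2 outcome only |
|---|---|---|
| 0.2 | 0.3% | 0 |
| 0.5 | 2.1% | 0 |
| 0.8 | 5.0% | 0 |

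A wider run took 0.46 and 0.30 as either two-year or annual rates, used between-year correlation 0 to 0.5, and let each year's attendance raise T6 self-efficacy by d:

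| d | T3 | T6 |
|---|---|---|
| 0.2 | under 1% | 1–3% |
| 0.5 | 2–4% | 8–14% |
| 0.8 | 5–9% | 19–30% |

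The zeros in the first table rest on independent years. If years are correlated, year-1 attendance is linked to both T3 self-efficacy and year-2 attendance, so splitting the outcome is not enough and year-1 attendance must also be in the model.

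**The case against.** The strongest reply is that section 12.4 is under-specified, not wrong. It never says that T3 or T6 self-efficacy will be related to two-year attendance, its mediation text gives no window for the binary summary, and it calls for causally preceding variables. Its worked example at parent level runs through illness representation. Attendance is scored by year and claims are abstracted after each visit, so a correct ordering is available. This stands in part. But the attendance summaries that section 12 defines cover two years, and against them no post-exposure self-efficacy value is correctly ordered. Detail alone does not cure that; the outcome for this path has to change.

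Four stronger readings are tempting, and the documents do not support them:

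- **That the planned path effects as a whole would not be mediation.** B1 has a two-week target in sections 5.5.2 and 7.2.2, and even day 120 is early in the window. The T-1 provider post-test precedes WCV #1, and the EMR audit, by section 8.1.4, starts at T0. Paths through these can be ordered correctly.
- **That the practice measures precede any exposure.** Section 7 puts randomization and finalized EMR changes before the T-1 activities. The order of the practice questionnaire relative to training is not given.
- **That late B1 returns spoil the illness-perception path.** This is minor, for the reason above.
- **That 65–79% (Arm A) and 59–74% (Arm B) of attenders precede T3.** These follow from p/[1 − ((1 − p)² + ρp(1 − p))] with ρ = 0 to 0.5, taking 0.46 and 0.30 as annual. The Arm B source is a past-year report, but section 12.2 applies both figures to two years. On neither reading is such a share the bias.

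It is also fair to say that the simulated bias for T3 is modest and that mediation is secondary.

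**Conclusion.** The concern holds for parent self-efficacy. No value of this mediator lies between first exposure and year-1 attendance, so relating T3 or T6 values to two-year attendance mixes cause and consequence. About 58% (Arm A) and 54% (Arm B) of eventual attenders would have attended by T3, assuming two-year rates of 0.46 and 0.30 and independent years of equal risk.

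The false mediated proportion is about 0.3% to 5% for T3 under assumed reverse effects of 0.2 to 0.8 SD. It is larger for T6, reaching 19–30% at 0.8 SD across the wider assumptions. The documents give no estimate of the reverse effect, so these figures show a range and do not predict the result.

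The same ordering rule applies to practice readiness, climate and attitude if they are collected at T2 (Day 364 ± 90). The primary analysis and the sample size are unaffected. This should be corrected before analysis.

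**What to change.** In section 12.4, name the mediator time point and the attendance interval for each path:

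- Pair T3 self-efficacy only with attendance from WCV #2 to WCV #3, counted from the date of WCV #2 and not from day 365, adjusted for T0 self-efficacy.
- Enter year-1 attendance in the path model as a causally preceding post-intervention variable, not as a baseline covariate.
- Do not use T6 mediators for attendance before T6.
- Use B1 illness perception at T1 as the parent mediator for year 1, with a sensitivity analysis excluding late returns. Starting the outcome at each B1 date would not work throughout, because the screening-based outcome only places a restoration or extraction between two visits.
- If practice readiness, climate and attitude are collected at T2, pair those scores only with year-2 attendance.
- Reconcile the practice and EMR time points in sections 8.1.3 and 8.1.4 with Table 8.1.1.

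The cost is SAP wording. Attendance by inter-visit interval is already planned (sections 3.2.1 and 8.1.1). The B1 sensitivity analysis needs a return date, which is assumed to be recorded because the forms are not available here. The downside is that year-1 effects through self-efficacy cannot be estimated. T3 self-efficacy, taken before the second encounter, also cannot carry that encounter's effect. The plan should declare both limits.
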